3. KEY ASSESSMENTS AND DERIVATIONS

3.1. Efficacy Assessments

3.1.1. Movement Disorder Society-Unified Parkinson's Disease Rating Scale (MDS-UPDRS)

The MDS-UPDRS (Goetz et al, 2008) is a multidimensional scale that assesses the motor and nonmotor impacts of PD across 4 parts. The scale is completed using a combination of physician and patient assessments and a collection of information from the patient or caregiver. Each evaluation item is rated on a scale from 0 to 4 on which 0 = normal, 1 = slight, 2 = mild, 3 = moderate, and 4 = severe. This trial incorporates Part I, II, and III assessments for the specific trial population.

3.1.1.1. Part I Score

Part I of the MDS-UPDRS focuses on the non-motor aspects of experiences of daily living. The MDS-UPDRS Part I score value for a given visit is obtained as the sum of all 13 evaluation items in the MDS-UPDRS Part I subscale, including the 6 items which are rated by the Physician. Valid values for the sum are integers from 0-52, with 0 being the least severe and 52 being the most severe.

3.1.1.2. Part II Score

Part II of the MDS-UPDRS focuses on the motor aspects of experiences of daily living. The MDS-UPDRS Part II score value for a given visit is obtained as the sum of all 13 evaluation items in the MDS-UPDRS Part II subscale. Valid values for the sum are integers from 0-52, with 0 being the least severe and 52 being the most severe.

3.1.1.3. Part III Score

Part III of the MDS-UPDRS is the motor evaluation comprises 18 items that are assessed by the investigator (resulting in 33 scores by location and lateralization). Valid values for the sum are integers from 0-132, with 0 being the least severe and 132 being the most severe.

3.1.1.4. Handling of Missing Items from MDS-UPDRS

If individual items are missing from a given part of the MDS-UPDRS, the corresponding total score may be generated by prorating the response if the number of missing items is not excessive. For Part I and Part II assessments, only a single missing item score is allowable. For Part III, up to 7 missing item scores are allowable. To prorate the value, the following formula is utilized

$$P = \left(\frac{\sum_{i=1}^n j_i}{n} \right) U$$

Where n is the number of non-missing items, j_1-j_n represents the n non-missing values reported by the subject for the given subscale, and U is the number of total items in the subscale. If more than the allowable items are missing, the total score will be treated as missing.

3.1.1.5. Part II + III Combined Score

The MDS-UPDRS Part II + III Combined Score is defined as the sum of the total scores for Part II and Part III within a given assessment (i.e., to have a Part II + III Total score, the subject must have a non-missing Part II total score and a non-missing Part III total score on the same date). The Part II + III Combined Score will be derived after any imputation of missing values within each individual total score.

3.1.1.6. Part I, Part II, and Part III Combined Score

The MDS-UPDRS Part I, Part II, and Part III Combined Score is defined as the sum of the total scores for Parts I, II, and III within a given assessment (i.e., to have a Part I, Part II, and Part III Combined score, the subject must have a non-missing Part I total score, a non-missing Part II total score, and a non-missing Part III total score on the same date). The Part I, Part II, and Part III Combined Score will be derived after any imputation of missing values within each individual total score.

3.1.2. Patient Global Impression of Change (PGIC)

The PGIC is the patient-reported outcome in a 7 point scale to rate how much the patient's illness has improved or worsened relative to the baseline state at the beginning of the intervention. The qualitative assessment of meaningful change is determined by the patient in response to the question, "Compared to your condition at the beginning of treatment, how much has your condition changed?" Scores are: 1=very much improved; 2=much improved; 3=minimally improved; 4=no change; 5=minimally worse; 6=much worse; and 7=very much worse.

3.1.3. Clinical Global Impression – Severity of Illness (CGI-S)

The CGI-S scale is a 7 point scale that requires the clinician to rate the severity of the patient's illness at the time of the assessment relative to the clinician's experience with patients who have the same diagnosis. Raters select one response based on the following question: "Considering your total clinical experience with this particular population, how ill is the patient at this time?" Scores are: 1=normal, not at all ill; 2=borderline ill; 3=mildly ill; 4=moderately ill; 5=markedly ill; 6=severely ill; and 7=among the most extremely ill patients.

3.1.4. Clinical Global Impression – Improvement (CGI-I)

The CGI-I is a 7 point scale that requires the clinician to assess how much the patient's illness has improved or worsened relative to the baseline state at the beginning of the intervention. Raters select one response based on the following question, "Compared to your patient's condition at the beginning of treatment, how much has your patient changed?" Scores are: 1=very much improved; 2=much improved; 3=minimally improved; 4=no change; 5=minimally worse; 6=much worse; and 7=very much worse.

3.1.5. 39-Item Parkinson's Disease Questionnaire (PDQ-39) Score

The 39-item Parkinson's Disease Questionnaire (PDQ-39) measures 39 items, which assess 8 domains of health: mobility (10 items), activities of daily living (6 items), emotional well being (6 items), stigma (4 items), social support (3 items), cognitions (4 items), communication (3 items), and bodily discomfort (3 items) (Peto et al, 1998). Each item is scored on the following scale: 0=never, 1=occasionally, 2=sometimes, 3=often, and 4=always. Items in each subscale and the total scale can be summarized into an index and transformed linearly to a scale from 0 (perfect health as assessed by the measure) to 100 (worst health as assessed by the measure).

A dimension score is calculated using the following formula:

$$d = \frac{1}{n * 4} \sum_{j=1}^n t_j * 100$$

where n is the number of items in the dimension, and t_j is the j^{th} item in the dimension. This transforms the scale linearly from 0 (perfect health as assessed by the measure) to 100 (worst health as assessed by the measure). If items are missing within a domain, the n in the above formula will be changed to the number of items in the dimension that the subject answered if at least half of the questions in the domain were answered. Otherwise, a domain and summary index will not be calculated.

A summary index called PDQ-39 SI, is calculated as the average of the 8-dimension scores.

3.1.6. EuroQol 5 Dimension 5 Level

The EuroQol 5 Dimension 5 Level (EQ 5D 5L) is a patient-reported outcome that measures health in 5 dimensions. It is a widely used survey instrument for measuring economic preferences for health states, is applicable to a wide variety of health conditions and treatments, and provides a simple descriptive profile and a single index value for health status (Herdman et al, 2011). The EQ 5D 5L consists of a descriptive system and a visual analog scale (VAS).

The descriptive system comprises 5 dimensions: mobility, self care, usual activities, pain/discomfort, and anxiety/depression. Each dimension has 5 levels: no problems, slight problems, moderate problems, severe problems, and extreme problems. The patient is asked to indicate his or her health state by ticking the box next to the most appropriate statement in each of the 5 dimensions (Section 9.2). This decision results in a 1 digit number that expresses the level that was selected for that dimension. The digits for the 5 dimensions are combined into a 5 digit number that describes the patient's health state. For example, 11122 would represent the health state for someone who has no problems with mobility, self-care, or usual activities, but who has slight pain or discomfort and slight anxiety or depression. For each subject and visit, the 5-digit health state will be converted into a single summary index, the EQ-5D Index, using the EQ-5D-5L Index calculator with US value set (van Hout, Janssen et al. 2012; Section 9.9).

The EQ VAS records the patient's self-rated health on a 20-cm vertical visual analogue scale (VAS). The VAS is numbered from 0 to 100 with 0 meaning 'the worst health you can imagine' and 100 meaning 'the best health you can imagine'. This information can be used as a quantitative measure of health outcome that reflects the patient's own judgement.

The EQ-5D-5L asks respondents to simply 'mark an X on the scale to indicate how your health is TODAY' and then to 'write the number you marked on the scale in the box below'.

3.1.7. Schwab and England Activities of Daily Living (ADL) Scale

The Schwab and England ADL scale is a method of assessing a person's ability to perform daily activities in terms of speed and independence through a percentage figure. The clinician determines the rating according to the following criteria, with 100% indicating total independence and 0% indicating a state of complete dependence:

- 100% Completely independent. Able to do all chores without slowness, difficulty, or impairment. Essentially normal. Unaware of any difficulty.
- 90% Completely independent. Able to do all chores with some degree of slowness, difficulty, and impairment. May take twice as long. Beginning to be aware of difficulty
- 80% Completely independent in most chores. Takes twice as long. Conscious of difficulty and slowness.
- 70% Not completely independent. More difficulty with some chores. Three to four times as long in some. May spend a large part of the day with chores.
- 60% Some dependency. Can do most chores, but exceedingly slowly and with much effort. Errors; some impossible.
- 50% More dependent. Help with half, slower, etc. Difficulty with everything.
- 40% Very dependent. Can assist with all chores, but few alone
- 30% With effort, now and then does a few chores alone or begins alone. Much help needed
- 20% Nothing alone. Can be a slight help with some chores. Severe invalid
- 10% Totally dependent, helpless. Complete invalid.
- 0% Vegetative functions such as swallowing, bladder and bowel functions are not functioning. Bedridden.

3.2. Safety Assessments

3.2.1. Questionnaire for Impulsive-Compulsive Disorders in Parkinson's Disease Rating Scale (QUIP-RS) Scores

The QUIP RS has 4 primary questions that pertain to commonly reported thoughts, urges/desires, and behaviors associated with impulse control disorders (ICDs), each of which is applied to 4 ICDs (compulsive gambling, buying, eating, sexual behavior) and 3 related disorders (medication use, punding, and hobbyism).

Each question is scored using a 5 point Likert scale (score, 0=never [not at all], 1=rarely [infrequently or 1 day/week], 2=sometimes, 3=often, 4=very often). Scores for each ICD and related disorder range from 0 to 16, with a higher score indicating greater severity (frequency) of symptoms.

The total QUIP-RS score for all ICDs and related disorders combined ranges from 0 to 112. In case of missing item scores, the missing value will be replaced by the average of non-missing scores at the same visit from the same subject. In case all item scores in any subcategory are missing, the total score will be set as missing.

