3.2.2. Epworth Sleepiness Scale (ESS) Total Score

The ESS scale is used to determine the level of daytime sleepiness. There are 8 situations listed for which patients rate their likelihood of dozing or sleeping (0=no chance of dozing, 1=slight chance of dozing, 2=moderate chance of dozing, or 3=high chance of dozing). The total score is the sum of 8 item scores and can range between 0 and 24. The higher total score indicates the higher level of daytime sleepiness. A score of 10 or more is considered sleepy, and a score of 18 or more is very sleepy.

In case of missing item scores from the ESS, the missing value will be replaced by the average of non-missing scores at the same visit from the same subject. In case all item scores are missing, the total score will be set as missing.

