5.14.2. Epworth Sleepiness Scale (ESS)

The ESS individual questions and total score and corresponding changes from baseline will be summarized by treatment group and study visit. The percentage of subjects with sleepy (10 or more) and very sleepy (18 or more) scores will also be summarized. ESS individual question score as well as the total score will be presented in a listing. The ESS total score will also be analyzed using the same method (MMRM analysis) described in [Section 5.9.2](#) to explore any treatment difference in sleepiness. Time curve plot will be presented for LSMean (SE) of change from baseline.

5.14.3. Questionnaire for Impulsive-Compulsive Disorders in Parkinson Disease Rating Scale (QUIP-RS)

The QUIP-RS component scores (Gambling, Sex, Buying, Eating, Hobbyism-Punding, PD Medication Use), total ICD score, and total score and corresponding changes from baseline will be summarized by treatment group and study visit. QUIP-RS individual data will be presented in a listing. The total ICD score will also be analyzed using the same method (MMRM analysis) described in [Section 5.9.2](#) to explore any treatment difference in impulsive-compulsive behaviors. Time curve plots will be presented for LSMean (SE) of change from baseline.

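### The missing-item rules for QUIP-RS and ESS can give misleading scores and are looser than the SAP's own rules for MDS-UPDRS and PDQ-39

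*SAP*

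**What the plan says.** SAP 3.2.1 describes QUIP-RS as four questions, "each of which is applied to 4 ICDs (compulsive gambling, buying, eating, sexual behavior) and 3 related disorders (medication use, punding, and hobbyism"). It adds: "Scores for each ICD and related disorder range from 0 to 16", and "The total QUIP-RS score for all ICDs and related disorders combined ranges from 0 to 112". For a missing item, "the missing value will be replaced by the average of non-missing scores at the same visit from the same subject". The only floor sets the total score to missing when every item of any one subcategory is missing. Subcategory is not defined: SAP 3.2.1 lists 7 disorders, while SAP 5.14.3 reports 6 components, with hobbyism and punding merged.

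SAP 3.2.2 uses the same replacement wording for the 8 ESS items and has one floor: "In case all item scores are missing, the total score will be set as missing".

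SAP 5.14.2 summarises the ESS total, the percentages scoring 10 or more and 18 or more, and an MMRM. SAP 5.14.3 summarises the QUIP-RS components, total ICD score and total score, and states: "The total ICD score will also be analyzed using the same method (MMRM analysis").

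The same SAP is stricter elsewhere. MDS-UPDRS (SAP 3.1.1.4) allows one missing item in Parts I and II and seven in Part III: "If more than the allowable items are missing, the total score will be treated as missing". PDQ-39 (SAP 3.1.5) averages the answered items of the same domain, and only "if at least half of the questions in the domain were answered".

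**The concern.** There are two gaps. First, no minimum number of ESS items is required, so a nearly blank form yields a complete-looking total that can fall on either side of the 10 and 18 cut-offs. Second, the QUIP-RS average is bounded by visit and subject but not by disorder. A problem confined to one disorder would then be diluted by zeros from the other six, and a disorder in which every answered item is 0 could receive a positive score.

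Protocol 1.1 and 2.1 name impulse control disorders and sleep disorders among the D2/D3-type effects that tavapadon aims to minimise. QUIP-RS and ESS are listed safety endpoints bearing on those aims, so their derived scores should not depend on how a sparse form happens to be filled.

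**Working it through.** **Stated ranges.** QUIP-RS: 4 items × maximum 4 = 16 per disorder; 16 × 7 = 112. ESS: 8 items × maximum 3 = 24. All agree with SAP 3.2.1 and 3.2.2. The answer patterns below are illustrative assumptions, because the documents contain no item data.

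**ESS.** With *k* items answered, summing to *s*, filling with the person's mean gives total = *s* + (8 − *k*) × *s*/*k* = 8*s*/*k*. The true total lies between *s* and *s* + 3(8 − *k*).

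| One item answered, scored | Imputed total | Possible true total | Category from imputed total |
|---|---|---|---|
| 0 | 0 | 0 to 21 | neither |
| 1 | 8 | 1 to 22 | neither |
| 2 | 16 | 2 to 23 | sleepy |
| 3 | 24 | 3 to 24 | very sleepy |

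The largest possible error is 3 points per missing item: 3 with one missing, 12 with four, 21 with seven.

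**QUIP-RS: mean of all answered items against mean within the disorder.**

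- Eating 4, 4, 4, missing; all else 0. The all-item mean is 12/27 = 0.44, so eating = 12.44. Within the disorder the mean is 4, so eating = 16. True value: 12 to 16.
- Gambling 0, 0, 0, missing; eating 4, 4, 4, 4; all else 0. The all-item mean is 16/27 = 0.59, so gambling = 0.59. Within the disorder, gambling = 0. True value: 0 to 4.
- Gambling 4 and three missing; all else 0. The all-item mean is 4/25 = 0.16, so gambling = 4 + 3 × 0.16 = 4.48. Within the disorder, gambling = 16. True value: 4 to 16.

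The literal rule can move a disorder score either way. The third pattern shows that a within-disorder mean alone is not enough: one answered item then sets the whole disorder score.

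**What the floor covers.** Suppose gambling is wholly blank, eating is 4, 4, 4, 4 and all else is 0. The total score is set to missing. Nothing sets the gambling component or the ICD score to missing. Read literally, each gambling item becomes 16/24 = 0.67, gambling becomes 4 × 0.67 = 2.67, and the ICD score becomes 16 + 2.67 = 18.67. This takes the ICD score as the sum of the four ICDs, which the SAP implies but does not define.

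**Tolerance for missing items across the SAP.**

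| Scale | Most items missing with a score still produced | Share |
|---|---|---|
| MDS-UPDRS Parts I and II | 1 of 13 | 8% |
| MDS-UPDRS Part III | 7 of 33 | 21% |
| PDQ-39 domain | half | 50% |
| QUIP-RS total, one answer in each of 7 disorders | 21 of 28 | 75% |
| ESS total | 7 of 8 | 88% |

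**The case against.** The strongest reply is that the QUIP-RS sentence gives no scope, so the cross-disorder average is a reading and not a settled fact. The floor fits a within-subcategory mean, since an empty subcategory would then have nothing to average. That reading is possible. Against it, SAP 3.2.2 uses identical wording for ESS, where it must mean every item of the scale, and SAP 3.1.5 states the restriction explicitly when a within-domain mean is wanted. Even if the reply is accepted, there is still no minimum number of answered items, and two programmers could derive different scores from the same form.

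A reader might infer that the eating score of 12.44 is 22% too low. That figure compares it with another imputation, (16 − 12.44)/16, and not with the truth; 12.44 lies within the possible range of 12 to 16. A reader might also infer that one answer suffices for a QUIP-RS total. It does not: at least one answer per subcategory is needed. The single-answer case applies to the ESS total and, under a within-disorder reading, to an individual disorder score.

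For ESS, filling with the person's mean is the same arithmetic as the prorating formula in SAP 3.1.1.4, so the method itself is sound and only the missing minimum is open to criticism. The striking examples need most items blank. ESS individual questions are summarised and listed and QUIP-RS individual data are listed, so the raw answers remain open to inspection. All of this stands, and it limits the size of the point.

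**Conclusion.** The point holds as a minor one. The ESS gap is plain in the text. The QUIP-RS rule is at best unscoped and, read literally, mixes disorders. Its floor does not reach the component scores or the modelled ICD score. Both rules are looser than those the SAP applies to MDS-UPDRS and PDQ-39, and no reason is given.

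The practical size is unknown, because the documents give no rate of missing items. With one ESS item missing, the total can be off by at most 3 points.

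A reader might infer that the rules favour tavapadon, or that they undermine the evidence for its claimed safety advantage. The documents support neither. The same rule applies in every arm, and nothing shows that missing items differ by arm. Hypotension and hallucinations are also named among the targeted harms, and adverse events and vital signs are analysed separately. Protocol Table 10 plans only descriptive summaries of the two scales, the SAP's models are exploratory, and neither scale is in the testing sequence of SAP 5.4. The primary and key secondary results are unaffected.

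**What to change.** **SAP 3.2.1.** Replace a missing QUIP-RS item by the mean of the answered items of the same disorder when at least 2 of its 4 items are answered. Otherwise set to missing that disorder score, any component that contains it (including the merged Hobbyism-Punding component), the total ICD score if the disorder is an ICD, and the total score. Define subcategory as each of the 7 disorders.

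**SAP 3.2.2.** Prorate the ESS total only when at least 4 of the 8 items are answered; otherwise set it to missing.

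This is the half rule already used for PDQ-39. It is a choice of tolerance and does not remove imputation error: the largest possible ESS error falls from 21 points to 12.

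The cost is a few sentences of SAP text and a small programming change. The downside is that some sparse forms become missing instead of scored.

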3.2.2. Epworth Sleepiness Scale (ESS) Total Score

The ESS scale is used to determine the level of daytime sleepiness. There are 8 situations listed for which patients rate their likelihood of dozing or sleeping (0=no chance of dozing, 1=slight chance of dozing, 2=moderate chance of dozing, or 3=high chance of dozing). The total score is the sum of 8 item scores and can range between 0 and 24. The higher total score indicates the higher level of daytime sleepiness. A score of 10 or more is considered sleepy, and a score of 18 or more is very sleepy.

In case of missing item scores from the ESS, the missing value will be replaced by the average of non-missing scores at the same visit from the same subject. In case all item scores are missing, the total score will be set as missing.

3.2.3. Adverse Event (AE)

An AE is defined as any untoward medical occurrence in a patient or clinical trial subject, temporally associated with the use of trial intervention, whether considered related to the trial intervention. NOTE: Signs and symptoms and/or abnormal laboratory test result indicating a common underlying pathology/diagnosis should be reported as a single AE.

All adverse events will be recorded on the ADVERSE EVENTS eCRF. Adverse events with missing severity will have the severity imputed as 'Severe' for the AE tabulations. Adverse events with missing relationship to IMP will have the relationship imputed as 'Related' for the AE tabulations if the AE started on or after the first dose of IMP. However, in the data listings these missing severity and/or relationship will be presented as missing.

3.2.3.1. Adverse Event of Special Interest (AESI)

For this study, any AEs related to abuse potential, AEs involving MHIs, abnormal liver function tests with a value $>3 \times$ ULN for ALT or AST and $>2 \times$ ULN for total bilirubin within the same visit, a value of $>3 \times$ ULN for ALT or AST and clinical jaundice, an AE leading to the discontinuation of IMP or from the study will be considered AESIs. These events will be noted by the investigator in the ADVERSE EVENTS eCRF.

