Investigators and site staff at each trial site will be trained on reporting potentially abuse-related AEs (eg, recording a description of the event in the subject's own words in the source documents as well as the eCRF, in addition to the clinical term, and to be aware that a subject's report may encompass more than one event and that these should be recorded separately). The investigators will be provided with examples of potentially abuse-related AEs and trained on how to handle such events (eg, additional monitoring).

While the investigators will be provided with examples of AE terms as a guide during trial conduct, the analysis of potentially abuse-related AEs will be based on a search by the sponsor of all relevant Medical Dictionary for Regulatory Activities (MedDRA) terms, all verbatim terms, and any open text fields within the AE data to identify text strings suggestive of abuse potential, consistent with US Food and Drug Administration (FDA) guidance (Guidance for Industry: Assessment of Abuse Potential of Drugs, January 2017).

Complete details, including documenting and reporting procedures, examples of potentially abuse-related terms and guidance for the training of investigators and trial site staff are provided in the APMP.

8.4.6.2 *Abnormal Liver Function Tests*

The finding of an elevated value for alanine aminotransferase (ALT) or aspartate aminotransferase (AST) of $>3 \times$ the upper limit of normal (ULN) in combination with either an elevated value for total bilirubin $>2 \times$ ULN or clinical jaundice in the absence of cholestasis or other causes of hyperbilirubinemia is considered to be an indicator of severe liver injury. Investigators must report the occurrence of either of the following as AESI to the sponsor with 24 hours:

- Treatment-emergent value of $>3 \times$ ULN for ALT or AST and $>2 \times$ ULN for total bilirubin
- Treatment-emergent value of $>3 \times$ ULN for ALT or AST and clinical jaundice

Brief narratives will be written for any subjects who experience abnormalities in liver function tests that meet the criteria specified above.

8.4.6.3 *Adverse Events Leading to Discontinuation*

Any AE that leads to discontinuation of IMP or from the trial will be classified as an AESI. Brief narratives will be written for subjects who discontinue IMP or from the trial because of AEs.

8.5 *Treatment of Overdose*

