The number and percentage of subjects who have post-baseline elevations in liver transaminase (alanine aminotransferase [ALT] or aspartate aminotransferase [AST]) or bilirubin abnormalities in relation to fold above the upper limit of normal will be summarized according to the Food and Drug Administration's Premarketing Clinical Evaluation on Drug-Induced Liver Injury Guidance for Industry ([FDA 2009](#)). Abnormal hepatic laboratory values will be categorized and evaluated for any occurrence among all post-baseline assessments (where "and" in the bulleted list below indicates elevations occurring at the same visit). Within each laboratory parameter grouping, a subject may be counted once per elevation criteria using the worst-case result.

That is, a subject with a worst case ALT elevation $> 5 \times$ the ULN would be counted once in the ALT $> 3 \times$ ULN category and once in the ALT $> 5 \times$ ULN category, regardless of how many ALT elevations the subject had that met the $> 3 \times$ ULN and $> 5 \times$ ULN elevation criteria.

- ALT and/or AST $> 3 \times$ ULN and total bilirubin > 1.5 or $2 \times$ ULN
- AST $> 3, 5, 10, 20 \times$ ULN
- ALT $> 3, 5, 10, 20 \times$ ULN
- Total bilirubin $> 1.5, 2 \times$ ULN
- Alkaline phosphatase (ALP) $> 1.5 \times$ ULN

In addition, an eDISH plot, a shift plot showing liver safety panel tests over time (baseline vs. post-baseline), and distribution plots of ALT, AST, ALP, and bilirubin over time will be produced to aid identification of any potential cases (Merz M. et. al. 2014). The plots to be included are the scatter plot of maximum transaminase versus maximum bilirubin, the liver test safety panel over time, and the distribution of ALT by time. The distribution plots for AST, ALP, and bilirubin will use the same format as used for ALT.

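### The SAP's combined transaminase-plus-bilirubin row and AESI definition require both elevations at one visit; the protocol AESI and the SAP's own eDISH plot do not, so a staggered case can count 0 in that row.

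*SAP*

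**What the plan says.** **Protocol 8.4.6.2 (Abnormal Liver Function Tests).** A transaminase above 3 × ULN "in combination with either an elevated value for total bilirubin" above 2 × ULN, or with clinical jaundice, is described as an indicator of severe liver injury. The section continues: "Investigators must report the occurrence of either of the following as AESI to the sponsor with 24 hours". The laboratory limb is "Treatment-emergent value of $>3 \times$ ULN for ALT or AST and $>2 \times$ ULN for total bilirubin". Timing between the two values is not mentioned.

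**SAP 3.2.3.1 (AESI).** The thresholds are the same, but the bilirubin limb adds "for total bilirubin within the same visit". The jaundice limb in the same sentence has no such condition. The section says that the investigator notes these events on the adverse event eCRF.

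**SAP 5.14.5 (Clinical Laboratory Assessments).** For the hepatic table, the word *and* "in the bulleted list below indicates elevations occurring at the same visit". This governs the row for ALT and/or AST above 3 × ULN with total bilirubin above 1.5 or 2 × ULN. The other rows cover AST, ALT, total bilirubin and ALP separately, over all post-baseline assessments: "Within each laboratory parameter grouping, a subject may be counted once per elevation criteria using the worst-case result". The same section plans a "scatter plot of maximum transaminase versus maximum bilirubin".

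**The concern.** Two rules for one safety signal stand in the same SAP section, and one of them is narrower than the protocol's wording. If bilirubin first rises at a repeat draw after the transaminase peak, the plot shows a subject above both limits while the combined row may report none. The protocol treats this pattern as a marker of severe liver injury, and very few cases would be expected, so one subject can be the whole content of the row. The SAP does not explain why it adds the condition, and it does not say what counts as one visit.

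**Working it through.** There is no stated figure to reproduce. The check compares the rules and applies them to constructed subjects.

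**1. Can the two values come from different draws?** The schedule of assessments places post-baseline safety blood at Weeks 11, 22 and 27 (Days 77, 154 and 189).
- Baseline to Week 11: 77 − 1 = 76 days
- Week 11 to Week 22: 154 − 77 = 77 days
- Week 22 to Week 27: 189 − 154 = 35 days

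Protocol 8.3.7 has clinically significant abnormal results repeated until they settle, and SAP 3.2.4 includes repeats in the laboratory reports. With scheduled draws this far apart, a staggered pattern would mostly be found through repeats.

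**2. Apply the rules to two hypothetical subjects.** All values are assumptions, in multiples of ULN.
- *Concurrent:* ALT 4 and bilirubin 2.5 at Week 11.
- *Staggered:* ALT 4 and bilirubin 1.2 at Week 11, then ALT 2.5 and bilirubin 2.6 at an unscheduled draw counted as a separate visit.

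| Output | Concurrent | Staggered |
|---|---|---|
| Combined row (ALT >3, bilirubin >2), same-visit rule | 1 | 0 |
| Combined row, maximum post-baseline values | 1 | 1 |
| ALT >3 row | 1 | 1 |
| Bilirubin >2 row | 1 | 1 |
| Above both thresholds on the plot | yes | yes |

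Only the combined row changes with the rule.

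**3. What is a visit?** SAP 4.2 maps unscheduled laboratory draws to the analysis windows of its Table 3. The Week 11 window is Days 67–86 (86 − 67 + 1 = 20 days), the Week 22 window is Days 141–168 (168 − 141 + 1 = 28 days), and Week 27 is Day 186 onward. Take an index draw on its target day.
- At Week 11, a repeat up to 86 − 77 = 9 days later keeps the Week 11 label.
- At Week 22, a repeat up to 168 − 154 = 14 days later keeps the Week 22 label.

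If visit means the analysis window, the staggered subject counts 1 when the repeat comes within those limits and 0 when it comes later. If visit means one draw, the count is 0 either way. Neither SAP 3.2.3.1 nor SAP 5.14.5 says which is meant.

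**4. Does the AESI summary change?** The flag is an investigator entry, and sites work from protocol 8.4.6.2, which has no visit condition. No step in the SAP removes a reported AESI because its two values came from different visits. The count falls only if the SAP wording is used to screen or reclassify events, or if sites are instructed by it.

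**The case against.** The defence has several sound parts.

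- **Scope.** A reader might infer that staggered cases disappear from the liver tables. They do not. Such a subject stays in the transaminase and bilirubin rows, the shift tables, the laboratory listings, the liver panel over time and the plot.
- **AESI reporting.** A reader might also infer that AESIs will be lost. The documents do not show this, because the investigator sets the flag under the protocol. An event leading to discontinuation, or a transaminase elevation with jaundice, also qualifies by separate limbs without a visit condition.
- **Protocol wording.** The protocol is silent on timing and does not say *at any time*. Its phrase "in combination with either an elevated value for total bilirubin" could be read as concurrent, so the SAP is narrower on wording and does not flatly contradict the protocol.
- **Purpose of the plot.** SAP 5.14.5 offers the plots as an aid to identifying potential cases. A subject seen there but absent from the combined row has still been brought to attention.
- **Cost of the alternative.** A maximum-against-maximum count could join a Week 11 transaminase rise to an unrelated Week 27 bilirubin rise, 189 − 77 = 112 days later. Exclusion criterion 25 admits some subjects with Gilbert's syndrome, whose bilirubin may be raised for other reasons.

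These points limit the consequence and argue against replacing the same-visit row. They leave three things unanswered: the unexplained difference from the protocol, the combined row and plot that can disagree on the same subject, and the undefined term.

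**Conclusion.** The point holds as a minor one on the consistency of safety reporting. SAP 3.2.3.1 and the combined row in SAP 5.14.5 impose a condition that protocol 8.4.6.2 does not state and the SAP's own plot does not apply. For a subject whose two elevations fall at different visits, the combined row can read 0 where a maximum-based row would read 1; every other liver output is unchanged. A zero is possible but not certain, since it depends on when the repeat was drawn and on how visit is programmed. An effect on the AESI summary is likewise possible but not shown. The documents give no basis for an expected number of such subjects. The conclusion rests on reading the protocol's silence on timing as no condition, and on at least one subject having staggered values. Efficacy analyses and the alpha allocation are not affected.

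**What to change.** Before database lock:

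1. In SAP 3.2.3.1, remove the same-visit phrase so that the AESI definition matches protocol 8.4.6.2.
2. In SAP 5.14.5, keep the same-visit row and state whether visit means the same draw or the analysis window of Table 3.
3. Add a second combined row based on each subject's maximum post-baseline transaminase and maximum post-baseline bilirubin, as on the plot.
4. List every subject above both thresholds, with dates and values of each elevation.

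The cost is a few SAP phrases, one table row and one short listing, all from data already collected. The drawback is that the maximum-based row may pair unrelated elevations weeks apart, so it should be read alongside the same-visit row and the listing and should not replace them.
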